1.3 Secondary Study Endpoints

Secondary outcomes for the study include changes in pulmonary function (FEV-1), tobacco-related toxicant concentrations, such as exhaled CO, EKG markers (HRV, PVCS, ST elevations, WRS duration),

urine cotinine, and blood pressure at 6 weeks, controlling for baseline measures. In addition, nicotine withdrawal and cravings, measured on the MNWS, at 1 week controlling for baseline. Finally, the average number of cigarettes smoked per day (CPD) and measures of dependence (e.g. FTND, PSECDI) will be analyzed. Outcomes at the 10 week telephone follow-up include the average number of cigarettes smoked per day in the week prior to the follow-up call, the number of days on which an e-cig was used in the previous 21 days, and the self-reported cigarette abstinence (zero cigarettes smoked in the prior week).

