- **7.2.2.3.5** Use of other tobacco products in the past 7 days will be assessed via Other Tobacco Use form. If the participant has used any other tobacco product in the past 7 days, they will be excluded.
- Participants will complete an exhaled carbon monoxide reading. Exhaled CO ≥6 ppm will be confirmed for inclusion in the study. Participants with a CO reading lower than 6 ppm will be excluded.
 - **7.2.2.3.6.1** When COVID protocols apply: Because this test requires that the participant remove their mask, the researcher will exit the room for this measure and will instruct the participant to complete the measurement via the two-way mirror and intercom system. Upon completing the measurement, the participant will be asked to put on their mask, and a timer for 15 minutes will be set as a guide for when the researcher may re-enter the room.
- **7.2.2.3.7** The participant will exit the clinic room to have their blood pressure measured. This is done in the small nursing station immediately outside of the clinic room. Participants with a blood pressure of systolic >159 mmHg or diastolic >99 mmHg will be excluded from the study.
- **7.2.2.3.8** Then the participant will have their height and weight measured.
- **7.2.2.3.9** Participants will then be taken to the CRC bathroom and will be asked to provide a urine sample. Participants unable to provide a urine sample will be excluded from randomization.
 - **7.2.3.9.1** Pregnancy exclusion will be confirmed through a urine test that will be self- administered by the participants when they come to this visit. Participants with confirmed pregnancy will be excluded.
- **7.2.2.4** The participant will then return to the clinic space. The researcher will remain outside the room to assess eligibility to continue with the study.
 - **7.2.2.4.1** If participants don't meet the eligibility criteria, they will be withdrawn from the study. They will be compensated for travel. The end of trial form will be completed. Eligible participants will continue with the study.

(Part B): Completion of Baseline Measures/Randomization

- **7.2.2.5** The 10 minute holter EKG procedure will be performed in the clinic space.
 - **7.2.2.5.1** When COVID protocols apply: This procedure will be completed once the clinic space is cleared for researcher entry (ie. 15 minutes after the CO measurement, measured using a timer).
- 7.2.2.6 Participants will then be randomized to a study group via REDCap.

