7.2.4 Switching Phase – Visit 2 (Day 21 ± 7 days)

The following procedures will be completed in a private clinic space in the Clinical Research Center. Participants and researchers will be wearing appropriate PPE at all times, except for noted measures where the participant will need to remove their mask (when COVID protocols apply).

Prior to the visit:

7.2.4.1 Participants will then be provided with instructions to complete measures via a home computer/smart phone (see table of measures). A link to the surveys in REDCap will be sent to the participant's email address or phone the day of the clinic visit. Participants will be instructed to complete all questionnaires within 24 hours. Participants unable to complete the questionnaires at home via a computer/smart phone will be called by the researchers to complete the questionnaires.

(Part A): Participant Check-In

7.2.4.2 The following measures will be completed:

- **7.2.4.2.1** Adverse events will be documented, and any concomitant medication changes will be recorded.
- **7.2.4.2.2** The cigarette and study product use diary will be collected by the researcher and entered into Daily Cigarette and E-cig Use Diary Log in Redcap.
- **7.2.4.2.3** Use of other tobacco products in the past 7 days will be assessed via the Other Tobacco Use form.
- **7.2.4.2.4** Participants will be encouraged to remain abstinent from cigarettes.
- **7.2.4.2.5** Participants will be instructed to complete daily diaries related to their study product and cigarette use (E-cigarette Daily Diary). They will also be asked to return all used and unused e-cig pods at their next study visit.
- **7.2.4.2.6** Participants will be provided with a supply of pods based on their usage.

(Part B): Completion of Biomeasures

- **7.2.4.3** The participant will then leave the clinic space to have their blood pressure and weight measured.
- **7.2.4.4** Participants will then be taken to the CRC bathroom and will be asked to provide a urine sample.
 - 7.2.4.4.1 A pregnancy test will be completed for women of childbearing potential.
 - **7.2.4.4.2** Participants will complete an exhaled carbon monoxide reading.

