7.2.6 Switching Phase – Visit 3 (Day 42 -7/+14 days)

The following procedures will be completed in a private clinic space in the Clinical Research Center. Participants and researchers will be wearing appropriate PPE at all times, except for noted measures where the participant will need to remove their mask (when COVID protocols apply).

Prior to the visit:

7.2.6.1 Participants will be provided with instructions to complete measures via a home computer/smart phone (see table of measures). A link to the surveys in REDCap will be sent to the participant's email address or phone the day of the clinic visit. Participants will be instructed to complete all questionnaires within 24 hours. Participants unable to complete the questionnaires at home via a computer/smart phone will be called by the researchers to complete the questionnaires.

(Part A): Participant Check-In

- **7.2.6.2** The following measures will be completed:
 - **7.2.6.2.1** Adverse events will be documented, and any concomitant medication changes will be recorded.

- **7.2.6.2.2** The cigarette and study product use diaries will be collected by the researcher and entered into the Daily Cigarette and E-cig Use Diary Log in Redcap. Participants will stop using the diaries at this point of the study forward.
- **7.2.6.2.3** Use of other tobacco will be assessed via the Other Tobacco Use form.
- **7.2.6.2.4** All used and unused e-cig pods will be collected by the researcher for review. Participants will then be able to retain some of the unused pods based on their usage.
- **7.2.6.2.5** Participants will be encouraged to remain abstinent from cigarettes.
- **7.2.6.2.6** Participants will also verbally be provided with information regarding how they can purchase their own e-cig devices and products, similar to the one used in the study. Participants will be instructed to purchase e-liquid from reputable companies and to not buy from unknown or illicit sources.

(Part B): Completion of Biomeasures

- **7.2.6.3** The participant will then leave the clinic space to have their blood pressure and weight measured.
- **7.2.6.4** Participants will then be taken to the CRC bathroom and will be asked to provide a urine sample.
 - **7.2.6.4.1** A pregnancy test for women of child-bearing age will be completed.
- **7.2.6.5** The participants will return to the clinic space to completed the 10 minute Holter EKG.
- 7.2.6.6 Participants will complete an exhaled carbon monoxide reading.

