COVID screening questions (day prior to visit)	x			Х			х			
Screening Questions	x									
Daily Cigarette and E-cig Use Diary	x	х	x	х	X	Х	х			
Past 7 day Cig and E-cig use								X	Х	
Other Tobacco Use	X	X	Х	Х	X	Х	X	X		
E-cig Patterns of Use and Log		X	Х	Х	X	Х	X	X		
Concomitant medications	X	X	Х	Х	X	Х	X	X		
Medical History	x	ĺ								
Cigarette Details	x									
Adverse events	X	X	Х	Х	X	Х	Х	X		
Demographics (Including Social Determinants of Health (SDOH))	x									
Tobacco use history	x									
Importance/Confidence to Quit	Х			Х		ľ	X	X		
NIDA drug screener (past 3 months)	x									
Environmental tobacco smoke	x			X			X			
Cigarette/E-cig perceived health risk	x			X						
E-cig Perceived Benefits and Harms	x									
Cigarette and E-cig Liking and Evaluation scales	x			X			x	x		х
Study Product Side Effects questionnaire		x	x	X	x	Х	x	x		х
Cigarette dependence (HONC, FTND, PSCDI)	x			X			x	x		
E-cig Dependence (Penn State E-cig DI)				X			x	x		
Questionnaire smoking urges	X	X	Х	Х	X	Х	X	X		х
Minnesota withdrawal scale	X	Х	X	Х	X	Х	Х	X		х
Audit-C	x						X			
CES-D	X			Х			Х			
Kessler K6	Х			Х			X			
Perceived stress scale	X			Х			X			

				0.	00100000	510
Clinical COPD questionnaire (CCQ)	X	X	X			
PROMIS Sleep Disturbance & Impact	x	X	X			
Interheart and WI Prepare	X		X			
Real World E-cig Use				Х		
Interview					Х	
Biomeasures/Procedures						
Weight	X	X	X			
Height	X					
Exhaled CO	X	X	X			x
Blood pressure/pulse	X	X	X			
Pulmonary function test (FEV1, FVC, PEF, FEF25, FEF75, FEF25-75, FET)	x	x	x			
Urine sample (NNAL, CYMA, MHBMA3, 3HPMA,8- isoprostanes, creatinine, cotinine)	x	x	x			
Holter EKG test (10 minutes)	X		X			
Pregnancy test	x	X	X			
Product use procedure			1			v

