8.3 Statistical methods

For the analysis, the baseline time will be Visit 1, prior to randomization to an e-cig nicotine content regimen (placebo or nicotine), which occurs at end of Visit 1.

Summary statistics will be provided for baseline smoking characteristics, along with other study demographics collected upon enrollment/screening at Visit 1. Summary statistics will also be provided for all variables at each visit. This will include all randomized subjects.

Aim 1: For each battery of measures, the mean change from week 1 to week 6 will be estimated with a corresponding 95% confidence interval. The p-value for testing zero underlying change will also be provided. This analysis will be conducted separately for the two treatment arms. To adjust for multiple comparisons, the false discovery approach will be used. Additionally, the trajectory of each measurement at visit 1 visit 2 and visit 3 will be modeled using linear mixed effects regression.

Aim 2: The difference between the two treatment arms on markers of health risk will be analyzed. The primary conceptual framework is a modified intent-to-treat: subjects will be analyzed by their randomized arm regardless of compliance with the e-cig nicotine content regimen, as long as data for the particular outcome is available at either of the post-randomization visits (Visit 2 or Visit 3). The basic statistical tool will be linear regression or logistic regression. Two sets of regressions will be conducted. The first set of regressions will model the dependence of the outcome measures at week 6 on the two treatment arms while controlling for the baseline value of the outcome variable. The second set of regressions will adjust for additional covariates at baseline (V1), to be selected via backward elimination at 0.05 significance level. These additional covariates will be chosen from the following list based on appropriateness for the specific outcome variable.

- Age
- Race
- Hispanic
- Education status
- Gender
- Income
- SDOH questionnaire (ACES score)
- Baseline cpd
- Baseline CO
- Baseline NNAL
- Baseline cotinine
- Menthol/non-menthol cigarettes
- Cigarette length
- Height
- Weight
- BMI

- Baseline FEV1
- Baseline PSCDI
- Quit attempt history
- "Currently, do you have any symptoms or a disease that you believe is caused or made worse by your tobacco use?" (yes/no)
- Perceived cessation support questions
- ETS questionnaire
- Baseline MNWS
- Baseline QSU
- Baseline audit c

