We will strive to minimize the number of missing values by rigorous follow-up with the study subjects. In spite of this, we still anticipate some missing values in the final datasets. Our basic tool to address this problem is multiple imputations. More specifically, if a variable is missing at V1, it will be imputed from the distribution of that variable of non-missing subjects. Due to the randomization at V1, non-missing subjects from both arms will be used for the distribution. For values missing at V3 (6 weeks after randomization), but non-missing at V2, the value collected at V2 will be carried forward in time via the LOCF (Last Observation Carried Forward) approach. For any instance where the participant remained in the trial, but did not provide data values at either post-randomization visit (V2 or V3), that case will be excluded from the analysis (modified ITT).

For some scenario, the missing values can be imputed by some reasonable assumptions. If a participant dropped out of the study prior to Visit 3 without providing Visit 2 data for the outcome, a 'worst-case-scenario' assumption will be made – assuming that the participant reverted back to exclusive smoking of cigarettes upon dropping out of the trial. Under this assumption, their Visit 2 baseline value will be carried forward to Visit 3. See the table below for a detailed outline of these methods:

V1	V2	V3	V` Baseline Result	V3 Endpoint Result	Mechanism of Missing		
+	+	+	Use directly Use directly		N/A		
+ + -			Lise directly	Impute V3 via LOCE from V2	Dropped out between V2 and V3		
	•	-			Missing V3 due to item non-response		
+	-	+	Use directly	Use directly	N/A		
-	+	+	Impute the V2 value from the overall sample distribution	Use directly	N/A		
			Use directly	Impute V3 via LOCF from V1	Dropped out between V1 and V2 Assume 'Worst-Case- Scenario'		
+	-	-	Excluded from Analysis (N	Dropped out between V2 and V3 Item Non-Response at V2			
			Excluded from Analysis (N	Completed the Switching Phase Missing V2 and V3 due to item non-response			
	Impute the V1 value		Impute the V1 value	Impute V2 via LOCE from V2	Dropped out between V2 and V3		
-	T	-	distribution		Missing V3 due to item non-response		
-	-	+	Impute the V1 value from the overall sample distribution	Use directly	N/A		
-	-	-	Excluded from Analysis (Modified ITT)				

Stratified Imputation Approach:

(+) = non-missing data(-) = missing data

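### Holter EKG is scheduled only at Visits 1 and 3, so the three-visit model and the Visit 2 fill in section 8.3 cannot apply to it, and the rules for EKG dropouts contradict each other

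*Combined protocol and SAP*

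**What the plan says.** **Status of the measure.** Section 1.3 lists "EKG markers (HRV, PVCS, ST elevations, WRS duration") among the secondary outcomes, to be assessed at 6 weeks with control for baseline. Section 1.1.1 puts the Holter EKG in the Aim 1 battery.

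**Schedule.** At Visit 1, section 7.2.2.5 states: "The 10 minute holter EKG procedure will be performed in the clinic space". At Visit 3, section 7.2.6.5 states: "The participants will return to the clinic space to completed the 10 minute Holter EKG". The Visit 2 biomeasures in section 7.2.4 start with "The participant will then leave the clinic space to have their blood pressure and weight measured" and go on to urine, pregnancy test, exhaled CO and lung function, with no EKG. In the Time and Events Table, the row "Holter EKG test (10 minutes") has two marks, while CO, blood pressure, lung function and urine have three.

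**Analysis (8.3).** For Aim 1, "the mean change from week 1 to week 6 will be estimated with a corresponding 95% confidence interval". In addition, "the trajectory of each measurement at visit 1 visit 2 and visit 3 will be modeled using linear mixed effects regression". For Aim 2, the week-6 value is regressed on arm and baseline. The Aim 2 modified intent-to-treat sentence admits a participant only if the outcome in question was observed at Visit 2 or Visit 3.

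**Missing data (8.3).** The text fills a missing Visit 3 value from Visit 2 where there is one. For anyone who leaves before Visit 3 without Visit 2 data on the outcome, it assumes a return to smoking and carries the baseline forward, although it labels that baseline as a Visit 2 value. For participants with a Visit 1 value only, the imputation table carries Visit 1 forward if they left between Visits 1 and 2. It excludes them if they left between Visits 2 and 3, in a row labelled "Dropped out between V2 and V3 Item Non-Response at V2".

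**The concern.** The plan treats Visit 2 as a source of data for every outcome. For EKG there is no Visit 2 value by design, so two parts of 8.3 have nothing to work on: the middle point of the trajectory, and the fill from Visit 2.

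The second is the more consequential. For a measure taken at all three visits, a late leaver normally has a Visit 2 value, and the rules agree on what to do with it. For EKG, no leaver has one. The pattern that the plan treats as early dropout or occasional item non-response becomes the pattern of every dropout with a baseline, and there the written rules disagree. Who is in the EKG analysis, and with what value, would then be settled by whichever passage the analyst follows, possibly after data have been seen.

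**Working it through.** **The plan's own figure.** Section 8.2 gives 120 per arm, dropout of up to 30%, a detectable NNAL difference of 35 and a post-treatment SD of 69.

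- Completers per arm: 120 × (1 − 0.30) = 84, as stated.
- Standard error: 69 × √(2/84) = 10.65. Ratio: 35 / 10.65 = 3.29. Two-sided 5% power: Φ(3.29 − 1.96) = 0.908, which matches the stated 90% or more. This takes the SD of 69 for both arms.

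The figure concerns NNAL, and urine is collected at all three visits. The documents give no sample-size figure for EKG.

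**What can be run for EKG.**

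- Aim 1 mean change: two time points. The week 1 in that sentence must mean Visit 1, since 8.3 sets baseline there. No Visit 2 value is needed.
- Aim 2 regression: Visit 3 on arm and Visit 1. No Visit 2 value is needed.
- Completers are observed at Visits 1 and 3, and the imputation table uses both values directly.
- Mixed model: with two visits it can be fitted, but it has no Visit 2 term. On simulated data for 84 people, a random-intercept model gave the same change and standard error as the paired analysis (−0.361, SE 0.089). It adds nothing to the mean change and shows no trajectory.

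**Dropouts with a baseline EKG, rule by rule.** Take 36 dropouts per arm (120 − 84), with every completer having both EKGs. Let p be the share of dropouts who leave before Visit 2. The documents do not give p, so its full range is shown.

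| Rule in 8.3 | Left before Visit 2 | Left between Visits 2 and 3 | EKG set per arm |
|---|---|---|---|
| Modified intent-to-treat sentence | Out | Out | 84 |
| Missing-data text | Baseline carried | Baseline carried | 84 + 36 = 120 |
| Imputation table | Baseline carried | Out | 84 + 36p |

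The table's count is 84 at p = 0, 93 at 0.25, 102 at 0.5, 111 at 0.75 and 120 at 1.

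**What the choice of rule does.** Assume that carried-forward cases show no change and that dropout is equal in both arms. The arm difference seen in completers is then retained in the proportion 84/n: 100% at n = 84, 82% at n = 102 (84/102) and 70% at n = 120 (84/120). With the SD held fixed, an effect of 0.50 SD, which has 90% power at 84 per arm, has power 0.90, 0.84 and 0.77 respectively. These figures compare the written rules with one another. They do not measure harm done by the EKG schedule.

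**The case against.** **The endpoint survives.** A reader might infer that the EKG endpoints cannot be analysed as the plan is written. The documents do not support that. The two analyses that answer the secondary outcome use Visits 1 and 3 only, and the trajectory model is introduced as an addition. This objection stands in full.

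**The split by date of leaving is not the whole plan.** A reader might infer that EKG dropouts are handled by when they left. That is true of the imputation table alone: the text makes no such split, and the modified intent-to-treat sentence drops everyone concerned. One could answer that the text refers to the table for detail, so the table governs. But the plan does not state any precedence, and the text and the table still say opposite things about people who leave between Visits 2 and 3. The plan's reason for carrying baseline forward, a presumed return to smoking, fits those people as well as the early leavers.

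**Most of the numerical bias is general.** A reader might put the shrinkage from carried-forward baselines down to the EKG schedule. Under the table, if half of the 72 dropouts leave early, 36/204 = 17.6% of the analysed EKG values are set to no change. For an outcome with Visit 2 data the share is 36/240 = 15.0%. With a quarter leaving early it is 18/186 = 9.7% against 18/240 = 7.5%, and with all leaving early it is 30% for both. The part specific to EKG is about 0 to 3 percentage points. Unequal timing shows the same thing. Suppose early and late loss are 10% and 20% on nicotine, and 20% and 10% on placebo. A change D common to both arms then appears as a difference of 22.2% − 12.5% = 9.7% of D for EKG. For an outcome whose Visit 2 value already shows D, it is 20% − 10% = 10% of D. The roughly 18% and 0.10 D figures therefore belong to the plan's declared worst-case rule and not to the missing Visit 2 EKG.

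**Other measures.** Audit-C and Interheart also appear to lack a Visit 2 mark, but they are not named endpoints in 1.3 and enter 8.3 only as baseline covariates. They are a side note.

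**Conclusion.** The point holds in a limited form. The Holter EKG has no Visit 2 measurement, and 8.3 does not allow for this. The three-visit trajectory cannot be produced for EKG, and the Visit 2 fill never applies.

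The substantive fault is that all EKG dropouts with a baseline fall where three written rules contradict each other. At 30% dropout the EKG set per arm is 84, 120, or somewhere from 84 to 120, according to the passage followed. That range rests on the plan's upper dropout figure, on complete EKG data among those who finish, and on dropout timing that the documents leave open. The label in the table's exclusion row also misdescribes these people, because no EKG was due at Visit 2.

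The disagreement over people who leave before Visit 2 is not peculiar to EKG. What is peculiar is that late leavers, who for other measures would usually have a Visit 2 value to carry forward, join it. The schedule does not affect the primary NNAL endpoint or its stated power. This should be corrected, and it does not threaten the trial's main result.

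**What to change.** In section 8.3:

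1. Limit the three-visit mixed model to measures scheduled at all three visits.
2. State that Holter EKG markers are analysed as Visit 3 adjusted for Visit 1.
3. Set one rule for a missing Visit 3 value of any measure not scheduled at Visit 2. Apply it the same way whenever the person left, and make the modified intent-to-treat sentence, the missing-data text and the imputation table agree with it.

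A suitable rule is multiple imputation, which the plan already calls its basic tool. It would use arm, the Visit 1 value, and the Visit 2 pulse, blood pressure, CO and cigarette data that are collected anyway, with baseline carry-forward kept as a sensitivity analysis. Any single rule, stated in advance, would end the contradiction.

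The cost is wording and slightly more analysis work, with no new visit or procedure. The drawback is that the Visit 2 measures only partly predict EKG markers, so the imputation will recover limited information.

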1.0 Objectives

1.1 Study Objectives

Our long term goal is to understand the likely health effects of cigarette smokers switching to a Standardized Research E-Cig (SREC) and to assess the role of nicotine delivery on switching, acceptability and markers of health outcomes. The specific objective of this proposal is to recruit a cohort of 240 current exclusive daily cigarette smokers and to measure a comprehensive battery of health markers at baseline and at 3 and 6 weeks after attempting to switch completely to SRECs containing either zero or 58 mg/ml nicotine in a randomized double-blind, placebo-controlled design with the following three specific aims:

- **1.1.1** Aim 1: To characterize the short-term effects of attempting to switch from traditional cigarette smoking to a Standardized Research E-Cig from baseline to 6 weeks using a comprehensive battery of measures (e.g. carcinogen biomarker (NNAL), pulmonary function testing, Holter EKG, exhaled CO, and cotinine, BP etc.).
 - **1.1.1.1** Our hypothesis is that attempting to switch to a SREC will result in a reduction in markers of harms to health, as compared with the baseline (exclusive cigarette smoking) measures.
- **1.1.2** Aim 2: To compare the effects of switching to a standardized research electronic cigarette (SREC) with pods containing 58 mg/ml nicotine liquid versus 0 mg/ml nicotine liquid on smoking behavior and changes in health markers at 6 weeks post-switching.
 - **1.1.2.1** Our hypothesis is that nicotine-containing SRECs will facilitate switching from smoking more efficiently than zero nicotine SRECs and will result in a significantly greater improvement in markers of health risk, but will conversely result in higher ratings of dependence on the SREC (as compared to the zero nicotine SREC) at 6 weeks post-switching (after controlling for baseline measures).
 - **1.1.2.2** We also hypothesize that the nicotine-containing SRECs, (as compared with the zero nicotine SRECs, after controlling for baseline) will result in a lower total score for the withdrawal items on the MNWS and lower mean scores on ratings of cigarette craving, during the first week of the trial.

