- 7.2.5 Switching Phase Phone Contact #3 (Day 28 ±7 days) and Phone Contact #4 (Day 35 ± 7 days) During each phone contact, daily study product and cigarette use will be collected, adverse events or changes to concomitant medications will be documented, and participants will be asked to verbally answer the measures indicated in the Time and Events Table during the phone call. Participants' answers will be entered directly into REDCap by the researcher at the time of the call. Participants will also be provided with advice/encouragement to remain abstinent from cigarettes. Participant's compensation for completing the phone call will be added to their Greenphire ClinCard.

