- Baseline cigarette perceived health rick score
- E-cig Perceived risk/Perceptions of e-cig risks (from screener)
- Baseline CESD
- Baseline Kessler 6
- Baseline perceived stress
- Baseline COPD questionnaire
- Baseline interheart
- Importance and confidence to quit

Same strategy will be used for withdrawal items on the MNWS and scores on ratings of cigarette craving. The analysis will be conducted for the values of these variables at week 3, however.

Cigarette Abstainers Subgroup Analysis

In addition to the intent-to-treat analysis, additional analysis on subgroup of regular cigarette abstainers only will be conducted. By design, this subgroup will only consist of Switching Phase Completers (still in the study at the time of V3) who have successfully abstained from cigarette and other tobacco use (except e-cigs) from 1 week prior to V2 consistently and consecutively until V3. Therefore, this subgroup would be defined as 'quit' for at least 4 weeks. Participants in this sub-group must also have an exhaled CO < 6 ppm at both V2 and V3. Based on our previous data, we believe that 40% of the nicotine e-cig group (84 x .40 = roughly 33 participants) and 20% of the placebo e-cig group (84 x .20 = roughly 16 participants) will be classified as abstainers. For this relatively small subgroup, we shall only model the dependence of the outcome measures at week 6 on the two treatment arms while controlling for the baseline value of the outcome variable. No elaborate adjustment of other covariates will be included.

Aim 3: The proportions of subjects who will try to abstain from cigarettes and who will continue to use an e-cig at week 10 will be compared between the two arms using Fisher's exact test. Switching Phase dropouts will be treated as 'non-abstainers' from cigarettes under the 'worst case-scenario' assumption. A supplementary logistic regression will also be conducted to explore their dependence on demographic variables in addition to the two treatment arms.

Multiple imputation for missing values

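### Withdrawal and craving are hypothesised at week 1 but compared at week 3, and no analysis rule uses the week 1 and week 2 phone scores of participants who leave early

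*Combined protocol and SAP*

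**What the plan says.** Section 1.1.2.2 predicts for nicotine against placebo, adjusting for baseline, a "lower total score for the withdrawal items on the MNWS and lower mean scores on ratings of cigarette craving" in the first week. Section 1.3 lists withdrawal and craving as a secondary outcome at 1 week. Section 8.3 sets out the Aim 2 regressions of the week 6 value on arm and baseline, then states "Same strategy will be used for withdrawal items on the MNWS and scores on ratings of cigarette craving", with the analysis at week 3. Week 3 is Visit 2.

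Section 8.3 has one missing-data scheme, worded for outcomes in general. A participant who drops out before Visit 3 with no Visit 2 value is handled by "assuming that the participant reverted back to exclusive smoking of cigarettes upon dropping out of the trial". The text continues: "Under this assumption, their Visit 2 baseline value will be carried forward to Visit 3". The table entry for dropout between Visits 1 and 2 is "Impute V3 via LOCF from V1". Section 8.3 also says that "the baseline time will be Visit 1, prior to randomization to an e-cig nicotine content regimen". Earlier in the same section, the modified intent-to-treat rule admits only participants with a value for the outcome at Visit 2 or Visit 3.

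In the Time and Events Table, the rows for the "Minnesota withdrawal scale" and for smoking urges are marked at Visit 1, at every phone contact and at Visits 2 and 3. Section 7.2.3 confirms that Phone Contacts #1 (Day 7 ± 7) and #2 (Day 14 ± 7) collect the measures marked for them.

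**The concern.** Three things do not fit together.

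- **Time point.** The hypothesis and the endpoint concern week 1, when Phone Contact #1 supplies the outcome directly. The planned comparison is two weeks later.
- **Meaning of worst case.** The rule suits NNAL, where the smoking-state value is the unfavourable one. Section 11.3 expects withdrawal symptoms after cigarettes are stopped, and section 7.2.2.7.3 starts the switch the morning after Visit 1. For these scales the Visit 1 score therefore records no rise at all.
- **Discarded data.** Someone who leaves shortly before Visit 2 may already have two post-switch scores. Neither the missing-data scheme nor the modified intent-to-treat rule takes account of them.

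At stake is a secondary hypothesis about early withdrawal. Participants with the worst withdrawal may be among those who leave before Visit 2, and their observed scores would not enter the comparison.

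**Working it through.** **The plan's own figure.** The only sizing statement (section 8.2) is for NNAL. Retention is 120 × 0.70 = 84 per group. For a difference of 35 and SD 69, the standardised difference is 35/69 = 0.507. Two-sided 5% power is Φ(0.507 × √(84/2) − 1.96) = Φ(1.327) = 0.908, which reproduces the stated 90% or more. No figure is given for MNWS or craving.

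**What happens to a participant lost before Visit 2**

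| Source in 8.3 | Treatment | Phone scores used? |
|---|---|---|
| Missing-data text and table | Visit 1 value assigned to Visit 3 | No |
| Modified intent-to-treat rule | Excluded, no Visit 2 or 3 value | No |
| Rule for a missing week 3 value | None written | No |

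The text's reference to a Visit 2 baseline cannot be literal, because the rule applies only when Visit 2 is missing. The table and the definition of baseline both point to Visit 1. The absence of a week 3 rule also affects participants with Visits 1 and 3 observed but Visit 2 missing: their Visit 3 value is used directly, and nothing is said about Visit 2.

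**Effect if Visit 1 is carried forward.** Let D be the mean rise from baseline and p the share lost before Visit 2 (0 = placebo, 1 = nicotine). Assume that those lost would have had their arm's mean rise. Each contributes zero change, so the expected arm difference is

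(1 − p0)D0 − (1 − p1)D1 = (D0 − D1) − (p0·D0 − p1·D1).

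Randomisation balances baseline in expectation, so baseline adjustment leaves this unchanged. At equal loss p the difference is (1 − p)(D0 − D1). In general it shrinks when p0·D0 > p1·D1, is unchanged at equality, and grows when the inequality reverses.

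Inputs: D0 = 4 and D1 = 2 are assumptions, as are the loss shares. Section 8.2 gives only an upper figure of 30% total dropout, not the share before Visit 2.

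| Loss, placebo/nicotine | Calculation | Difference (true 2.0) |
|---|---|---|
| 15%/15% | 0.85×4 − 0.85×2 = 3.4 − 1.7 | 1.7 |
| 20%/10% | 0.80×4 − 0.90×2 = 3.2 − 1.8 | 1.4 |
| 10%/20% | 0.90×4 − 0.80×2 = 3.6 − 1.6 | 2.0 |
| 10%/30% | 0.90×4 − 0.70×2 = 3.6 − 1.4 | 2.2 |

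With these rises the break-even is p1 = 2·p0.

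**Power, for illustration.** Assume rises of 0.6 SD (placebo) and 0.2 SD (nicotine), so a true difference of 0.40 SD, with the SD held at 1. Power at 120 per arm with no loss is 87%.

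| Loss, placebo/nicotine | Visit 1 carried forward | Excluded, difference still 0.40 SD |
|---|---|---|
| 10%/10% | 0.36 SD, 80% | 84% |
| 20%/10% | 0.30 SD, 64% | 81% |
| 10%/30% | 0.9×0.6 − 0.7×0.2 = 0.40 SD, 87% | not calculated |

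The exclusion column assumes that those who leave do not differ from those who stay. That is the assumption in doubt if withdrawal drives dropout.

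**The case against.** A reader might infer that the plan scores early dropouts as having no switch-related withdrawal, and so biases the comparison towards no difference. The documents do not support that as a statement of fact.

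- **The carry-forward rule is not written for week 3.** Every endpoint rule fills a missing Visit 3. The sentence extending the strategy to these scales follows the regression and covariate description, and the missing-data text comes later under its own heading. Applying the Visit 1 rule here is one reading.
- **The modified intent-to-treat rule would exclude the same people.** The attenuation formula then does not apply.
- **A Visit 1 score is coherent at week 3 for someone who has truly resumed smoking.** What is lost is the withdrawal felt before leaving, not necessarily the week 3 state.
- **The direction is conditional.** If early loss is sufficiently higher on nicotine, the difference is unchanged or inflated, as the last two rows of the first calculation show.
- **The smoking-state reading of Visit 1 has a limit.** Section 7.2.2.9 allows home questionnaires up to 24 hours after the visit. If the MNWS is among them, some baseline scores could follow the start of the switch.

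All of these stand. They limit the bias claim but do not restore the phone scores: no reading of section 8.3 brings them into the comparison. Nor do they reconcile the week 1 hypothesis with the week 3 analysis.

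**Conclusion.** The point holds in three parts that need no assumption. The time of the comparison contradicts the hypothesis and the endpoint. Section 8.3 gives conflicting treatments of participants lost before Visit 2 and has no rule for a missing week 3 value. The Phone Contact #1 and #2 scores are unused under every reading.

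A fourth part is conditional. If Visit 1 is carried forward, the change is exactly zero for each affected participant, so the worst-case label does not fit withdrawal. Under the assumed rises and losses, the true difference of 2.0 becomes anything from 1.4 to 2.2. Shrinkage is certain at equal early loss when the placebo rise is larger, as hypothesised; it is not certain otherwise. Only participants without a Visit 2 value are affected. This concerns a secondary outcome and leaves the NNAL comparison untouched, but it should be corrected because the remedy is cheap.

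**What to change.** In section 8.3:

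1. Exempt MNWS and smoking-urge scores from the Visit 1 carry-forward rule, and reconcile the modified intent-to-treat definition with the missing-data scheme for them. Any participant with a post-switch score at a phone contact or visit should contribute.
2. Analyse each scale with a baseline-adjusted mixed model over all scheduled contacts (Visit 1, Phone Contacts #1 and #2, Visit 2 and later), with contact categorical and an arm-by-contact term.
3. Make the week 1 contrast (Phone Contact #1) the main one, to match sections 1.1.2.2 and 1.3, with the week 3 contrast as supporting.
4. Keep Visit 1 carry-forward only as a sensitivity analysis.

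The cost is SAP wording, one more model per scale and a missing-at-random assumption, which should be stated. No new data are needed, and section 8.3 already plans linear mixed models for the Aim 1 trajectories.
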